6.5.4.5 Immune cell-associated neurotoxicity syndrome (ICANS)

Immune cell-associated neurotoxicity syndrome (ICANS) is a neuropsychiatric syndrome which is frequently associated with CRS; however, it is specifically excluded from the definition of CRS and can occur during the course of CRS, after its resolution, or independently from CRS. Clinical findings can be progressive and may include aphasia, altered level of consciousness, impairment of cognitive skills, motor weakness, seizure, and cerebral edema. Severity is evaluated using the ASTCT Consensus grading scale, with ICE score for encephalopathy assessment (Section 10.11 of the master protocol). Recommendations for ICANS management mainly include the use of steroids, whereas tocilizumab should only be used in the context of CRS, as outlined in [Table 7](#). The proposed management should be considered only as recommendations and in light of recommendations from site specialist.

Table 7 - Guidelines for the management of immune cell-associated neurotoxicity syndrome (ICANS)

Event severity (ASTCT Consensus Grading criteria)	Recommended SAR444245 dose modification and supportive care guidelines
Mild Grade 1 ICE score 7-9. Awakens spontaneously	No intervention required other than close clinical monitoring.

Event severity (ASTCT Consensus Grading criteria)	Recommended SAR444245 dose modification and supportive care guidelines
Moderate Grade 2 ICE score 3-6. Awakens to voice.	SAR444245 ^a should be delayed. Treatment with IV corticosteroids should be initiated as needed. SAR444245 may be resumed only after participant recovery or improvement to Grade 1 after corticosteroid taper. Consideration for reduction of SAR444245 dose to █ µg/kg as per Investigator with Sponsor consultation.
Severe or Life-threatening Grade 3 ICE score 0-2. Awakens only to tactile stimulus. Any clinical seizure focal or generalized that resolves rapidly or nonconvulsive seizures on EEG that resolve with intervention. Grade 4 ICE score: 0 (participant is unarousable and unable to perform ICE). Participant is unarousable or requires vigorous or repetitive tactile stimuli to arouse. Stupor or coma. Life-threatening prolonged seizure (>5 min): or Repetitive clinical or electrical seizures without return to baseline in between. Deep focal motor weakness such as hemiparesis or paraparesis. Diffuse cerebral edema on neuroimaging; decerebrate or decorticate posturing; or cranial nerve VI palsy; or papilledema; or Cushing's triad.	If Grade 3 ICANS, SAR444245 should be delayed. When symptoms have resolved or improved to Grade 1 after corticosteroid taper, SAR444245 can be either restarted at █ µg/kg or permanently discontinued, as clinically indicated, and upon discussions between the Investigator and Sponsor. If Grade 4 ICANS, SAR444245 should be permanently discontinued. Treatment with IV corticosteroids should be initiated. Concomitant CRS may require tocilizumab and should be handled as described in Table 5 in Section 6.5.4.3 . Corticosteroids can then be administered IV or orally every 8 hours for up to 3 days, then tapered over 4 days. For both Grade 3 and Grade 4 ICANS If there is no clinical improvement within 24 to 72 hours, then re-evaluation for other contributing conditions should be done. Administration of IV Tocilizumab at 8 mg/kg (for participants weighing ≥30 kg, total dose should not exceed 800 mg) should be considered, and steroids should be administered concurrently and repeated as previously mentioned for CRS. Neurologist and other relevant clinical specialists should be involved whenever indicated.

^a Information for preparation and storage of SAR444245 is provided in the pharmacy manual

Abbreviations: ASTCT=American Society for Transplantation and Cellular Therapy; CRS= cytokine release syndrome; ICANS= Immune effector cell associated neurotoxicity syndrome; ICE= Immune Effector Cell-Associated Encephalopathy; IV = Intravenous.

6.5.4.6 Vascular leak syndrome (VLS)

Vascular leak syndrome is a disorder characterized by leakage of intravascular fluids into the extravascular space and can lead to generalized edema and multiple organ failure. This syndrome is observed in patients who demonstrate a state of generalized leaky capillaries following shock syndromes, low-flow states, ischemia-reperfusion injuries, toxemias, medications, or poisoning. In various human diseases, an increase in capillary permeability to proteins leads to the loss of protein-rich fluid from the intravascular to the interstitial space manifested by any of the following **clinical presentations: diffuse pitting edema, exudative serous cavity effusions, noncardiogenic pulmonary edema, hypotension, and, in some cases, hypovolemic shock with multiple-organ failure**. Fluid management is the cornerstone of VLS management; it is a balance between maintaining the intravascular volume to ensure organ perfusion to prevent organ failure, while avoiding volume overload. The management of VLS according to severity grading is described in [Table 8](#). These guidelines are not comprehensive and the Investigator should exercise clinical judgment based on the symptoms and condition of the individual participant and refer to current guidelines to the topic (1).

Table 8 - Guidelines for the management of vascular leak syndrome (VLS)

Event severity (NCI-CTCAE V5.0)	Recommended IMP dose modification and supportive care guidelines
Mild Grade 1 Asymptomatic	No intervention required other than clinical monitoring.
Moderate Grade 2 Symptomatic; medical intervention indicated	SAR444245 should be delayed. Upon resolution of VLS or improvement to Grade 1 , SAR444245 ^a can be resumed at the reduced dose of █ kg. The initial strategy is to administer boluses of crystalloids with a goal of providing the minimum effective volume that optimizes blood pressure together with a fluid-restrictive strategy is advocated to limit interstitial fluid volume expansion.
Severe or Life-threatening Grade 3: Severe symptoms; intervention indicated Grade 4: Life-threatening consequences; urgent intervention indicated	
If Grade 3 or Grade 4 VLS, SAR444245 should be permanently discontinued.
 
In participants with severe shock, blood pressure may be only partially responsive or refractory to IV crystalloid fluids.
 
Severe or persistent hypotension is to be managed by the administration of vasopressors. A trial of 25% albumin IV is an additional option, although its efficacy is limited to those with a severe capillary leak. In those who remain with refractory shock in the setting of low filling pressures, high molecular weight starches such as hetastarch (MW 450 kDa) and pentastarch (MW 264 kDa) may be effective in expanding the intravascular volume. Supportive care with invasive and noninvasive ventilation as well as renal replacement may be necessary in severe cases. When available, disease-specific therapy should be initiated as soon as possible to facilitate recovery.
 
During the recovery phase from severe capillary leak, the endothelial injury resolves and the capillary leak becomes less important, resulting in stabilization of blood pressure, at which time fluid overload symptoms and signs may predominate (eg, pulmonary edema, pleural effusions, acute respiratory distress syndrome, systemic edema, ascites). Volume removal with loop diuretics is the first-line therapy in these patients. In those with marginal blood pressure and fluid overload, the combination of loop diuretics and 25% albumin IV may facilitate volume removal. Patients with AKI refractory to diuretics will require renal replacement.

a Information for preparation and storage of SAR444245 is provided in the pharmacy manual.

Abbreviations: AKI= acute kidney injury; CTCAE = Common terminology criteria for adverse events; IV = Intravenous; MW= molecular weight; NCI = National Cancer Institute; VLS= vascular leak syndrome.

6.5.4.7 Hepatic Events

Hepatic events (HEs) as described in [Section 8.3.8](#). All these HEs will require holding study intervention with an immediate assessment:

All participants should be considered for evaluation according to the directions below within 72 hours of the alert for AESI.

- Procedures:
 - Consider obtaining a consultation with a hepatologist

- Obtain a work-up for hepatitis if there is no underlying hepatitis, including hepatitis A, B, C, D, E, Epstein-Barr virus, and cytomegalovirus
- Assess for ingestion of drugs/supplements with hepatotoxic potential
- Assess for alcohol ingestion
- Assess for potential bacterial infection, biliary obstruction, or occult gastrointestinal bleeding
- Repeat ALT, AST, total bilirubin, direct bilirubin, alkaline phosphatase, γ -glutamyl transpeptidase, INR, and complete blood count with differential
- Measure HCV RNA viral load (applies only for participants who have current active HCV infection or had infection in the past)
- HBV DNA, HBsAg, HBeAg, anti-HBc (total and IgM), anti-HBe, and anti-HBs regardless of prior HBV status (Note: participants should be questioned about compliance with the use of antiviral agents)
- Other laboratories or imaging studies as clinically indicated
- Consider liver biopsy if indicated

HCC patients are at risk for a range of complications that can cause hepatic laboratory abnormalities with or without clinical decompensation. Those with a history of chronic HCV or HBV infection also have the potential to experience virologic flares. Immune-related hepatitis has been observed in approximately 1-2% of participants who received pembrolizumab. The following section provides further guidance on the diagnosis and management of potential hepatic complications among HCC participants in this study. The recommendation is to hold study interventions (cycle delay when SAR444245 is withhold + pembrolizumab is withhold). If toxicity does not improve within 1 to 2 days or worsens, follow “Management of HE for Pembrolizumab/SAR444245” below.

Table 9 - Management of HE associated with Pembrolizumab and SAR444245

Diagnosis	Management
Hepatitis B consider flare or change in HBV immunologic status	
Rapid elevation of ALT to $>5 \times$ ULN and/or $>3 \times$ baseline
 
Interrupt pembrolizumab and SAR444245 interventions for up to 12 weeks.
 
Start antiviral therapy or check for compliance if HBV is detectable.
 
Measure safety labs for AST, ALT, ALP, T Bili, D Bili, and INR on weekly basis.
 
Measure HBsAg and HBV DNA on weekly basis (if detected at the time of onset of ECI).
 
Evaluate the following every 2-3 weeks:
 
anti-HBe, HBe antigen, anti-HBs, and HBV DNA levels (if not detected at the onset of ECI)
 
Restart pembrolizumab and SAR444245 intervention only if ALT returns to normal or Grade 1 (if normal at baseline), or to baseline grade (if Grade 2 at baseline) within 12 weeks, and the participant is clinically stable; otherwise, the participant should have permanent full discontinuation of study interventions

Diagnosis		Management
Hepatitis C exacerbation in participants with HCV RNA positive	Rapid elevation of ALT to $>5 \times$ ULN and/or >3 times baseline	Interrupt pembrolizumab and SAR444245 interventions for up to 12 weeks. Assess use of injection or inhalation drugs.
Relapse of HCV infection for participants with successfully treated or new HCV infection	If HCV RNA was TND at baseline, and now has confirmed detectable HCV RNA (2 specimens, 1 week apart)	Recheck HCV genotype at the time of relapse of HCV RNA to rule out new infection. Measure safety labs for AST, ALT, ALP, T Bili, D Bili, and INR on weekly basis Measure HCV RNA levels every 2 weeks. Please discuss risk benefit with Sponsor prior to starting HCV antiviral therapy. Restart pembrolizumab and SAR444245 interventions only if ALT returns to normal or Grade 1 (if normal at baseline), or to baseline grade (if Grade 2 at baseline) within 12 weeks, and the participant is clinically stable; otherwise, the participant should have a permanent full discontinuation of study interventions.
Immune-related Hepatitis	If any of the HECL criteria is met as defined in the protocol Section 8.3.8 Note: Immune-related hepatitis is a diagnosis made after excluding other possible etiologies such as viral flare, biliary or vascular obstruction, infection, medications, and alcohol use usually immune-related hepatitis response to dechallenge and/or steroids and re-occurs with rechallenge	Interrupt pembrolizumab and SAR444245 interventions for up to 12 weeks. Start IV corticosteroid 60 mg/day of prednisone or equivalent followed by oral corticosteroid. Monitor with biweekly laboratory tests, including AST, ALT, T Bili, D Bili, ALP, and INR. Restart pembrolizumab and SAR444245 intervention only if: Abnormal laboratory values resolve to Grade ≤ 1 or baseline (if abnormal at baseline) Taper steroid over 28 days Steroid treatment is tapered to prednisone <10 mg/day or equivalent Permanently fully Discontinue pembrolizumab and SAR444245 intervention if: Laboratory abnormalities do not resolve within 3 weeks Steroids cannot be lowered to ≤ 10 mg/day (or prednisone equivalent) within 12 weeks Decompensation to CP-C status
Other Causes	Rule out infection with blood, urine, and ascites culture - antibiotics should be started if infection is found If total bilirubin is elevated, imaging should be obtained to rule out vascular compromise, biliary obstruction, and/or tumor progression by imaging Ruled out alcohol use and hepatotoxic drugs including herbal and alternative medications	Restart pembrolizumab and SAR444245 only if laboratory values have returned to Grade 1 or baseline (if normal or Grade 1 at start) or to baseline grade within 3 weeks. If biliary obstruction is present, consultation with a gastroenterologist and/or an interventional radiologist should be obtained to see if the obstruction may be relieved.

Abbreviations: ALT= alanine aminotransferase; ALP=alkaline phosphatase; AST=aspartate aminotransferase; D Bili=direct bilirubin, HBe= hepatitis B e antigen; HBs= hepatitis B surface antigen; HBV= hepatitis B virus; HCV= hepatitis C virus; HECl= Hepatic Events of Clinical Interest; INR= international normalized ratio, IV=intravenous; T Bili=total bilirubin, TND= target not detected.

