6.5 DOSE MODIFICATION

6.5.1 General rules

Dose modifications for SAR444245 are permitted according to the guidelines described in this section. Pembrolizumab dose reductions are not permitted. Pembrolizumab treatment may be interrupted or discontinued due to toxicity.

Dose modifications different from those stated in the protocol should only be made in consultation with the Sponsor, unless required for immediate participant safety.

Cycle delay (ie, Day 1 should be delayed for all IMPs) is permitted in case of treatment-emergent adverse event (TEAE). Dose modification will be made according to the worst grade of toxicity observed within a cycle. If a participant experiences several toxicities and there are conflicting recommendations, the most conservative recommended dose adjustment should be followed.

In participants who have SAR444245 dose reduction due to SAR444245 related Grade ≥ 3 treatment-related adverse events (TRAEs), SAR444245 dose may be re-escalated to █ $\mu\text{g}/\text{kg}$ if:

- no SAR444245 related Grade ≥ 3 TRAE or clinically significant laboratory abnormality within at least 2 subsequent cycles, AND
- both Investigator and Sponsor agree that the participant has clinical benefit.

Administration of the study treatment will be discontinued in the event of a TEAE that persists despite appropriate dose modifications or any other TEAE that, in the opinion of the Investigator, warrants discontinuation.

If any of the IMP components is permanently discontinued, the other IMP component can be continued until disease progression or other criteria as detailed in Section 7.1.1 of the master protocol are met. In this case, it is partial permanent discontinuation, and the end of treatment (EOT) assessment will be 30 days after the date of the last administration of the remaining IMP. When all IMP components are permanently discontinued, it is full permanent discontinuation.

All changes to study treatment administration must be recorded in the electronic case report form (e-CRF).

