6.5.2 Cycle delay

The treatment window is ± 3 days for each of the Q3W administrations. A cycle is deemed to have been delayed if the treatment is administered ≥ 4 days beyond the theoretical day of Q3W IMP administration. The participant may receive the next dose after recovery from the toxicity as described in [Section 6.5.3](#) and [Section 6.5.4](#). After cycle is delayed, such participants may be considered for treatment resumption once the toxicity resolves or improves to Grade 1 or baseline.

Participants may have cycle delay, if toxicity occurs and the participant does not recover according to following rules:

- For Q3W IMP administration: If toxicity occurs and the participant does not recover on the day of planned administration, the cycle will be delayed; restart of study IMPs could occur only on the initiation of the subsequent cycle.
- In case of cycle delay for the recovery of toxicity, the following rules should be followed for restart or discontinuation of the treatment:
 - In case of a cycle delay up to 14 days, it is per Investigator's decision to restart the study treatment.
 - After a cycle delay of >14 days and ≤ 84 days, it is per Investigator's decision to restart the study treatment, if a clear benefit from treatment is observed and after consultation with the Sponsor.
 - The study treatment must be permanently discontinued if the cycle delay is longer than 84 days.

- Cycle may be delayed for situations other than TEAEs such as medical/surgical events or logistical reasons not related to study therapy. Participants should be placed back on study therapy within 21 days of the scheduled delay, unless otherwise discussed with the Sponsor (for example for national or regional emergencies). The reason for the delay should be documented in the participant's study record.

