6.5.3 General guidelines for the management of treatment-related adverse events

Participants who experience Grade ≥ 3 TRAEs at any time of the study (including clinically significant Grade 3 laboratory abnormalities as defined in Section 10.3.1 of the master protocol) not listed in [Section 6.5.4](#) (Tables 3-8) will be required to temporarily delay the IMP. After cycle delay, such participants may be considered for treatment resumption once the TRAE resolves or improves to Grade 1 or baseline.

The dose of SAR444245 should be reduced to █ µg/kg (with the exception of lymphocytopenia which is directly associated with SAR444245 mode-of-action and does not require dose reduction) in cases of:

- First occurrence of Grade 3 TRAE that does not resolve to Grade 1 or baseline within 72 hours, and second occurrence of Grade 3 TRAE of any duration.
- Grade 4 TRAE.
- First occurrence of Grade 3 laboratory abnormality that are clinically significant per Section 10.3.1 of the master protocol. and that do not resolve to Grade 1 or baseline within 72 hours, and second occurrence of Grade 3 clinically significant laboratory abnormality of any duration.
- Grade 4 laboratory abnormalities that are clinically significant.

Treatment resumption is at the discretion of the Investigator and Sponsor, if thought to be in the best interest of the participant, except when specified otherwise in this protocol, or if the event has required the IMP temporary interruption for more than 84 days from the last scheduled dose.

The cycle delay of treatment for Grade 2 events is left at the discretion of the Investigator unless otherwise specified in this protocol.

No cycle delay of treatment or dose modification is required for Grade 1 events.

The final decision on dose modification and/or corrective therapy will be based on the Investigator's judgment, in the best interest of the participant.

Recommended guidelines for the management of specific adverse events including irAE, CRS, Vascular Leak Syndrome (VLS) and Infusion-related reactions (IRR) are presented in [Section 6.5.4](#).

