8.3.8 Adverse event of special interest

Please refer to the master protocol.

Hepatic Events (HEs) include any of the following events if the events are considered not due to disease progression as judged by the investigator

- ALT:
 - a) Among subjects with Baseline ALT $<2 \times$ ULN: ALT $\geq 5 \times$ ULN
 - b) Among subjects with Baseline ALT $\geq 2 \times$ ULN: ALT $>3 \times$ the Baseline level
 - c) ALT >500 U/L regardless of baseline level
- Total Bilirubin:
 - a) Total bilirubin >3.0 mg/dL
- Regardless of laboratory values, hepatic decompensation diagnosed clinically, including:
 - New onset clinically detectable ascites requiring intervention for >3 days

- Hepatic Encephalopathy

In addition, symptomatic or asymptomatic overdose with pembrolizumab are described as below:

- An overdose of pembrolizumab will be defined as any dose of 1000 mg or greater.

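### Substudy 03, Table 9: the hepatitis B and C restart rules omit a Grade 1 baseline ALT, so full recovery to that baseline leads to permanent discontinuation

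*Protocol*

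**What the plan says.** All references are to the Protocol, substudy 03 (Cohort C, hepatocellular carcinoma).

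- **Section 6.5.4.7, Table 9, hepatitis B and hepatitis C rows.** Both rows carry the same ALT condition. Pembrolizumab and SAR444245 may restart "only if ALT returns to normal or Grade 1 (if normal at baseline), or to baseline grade (if Grade 2 at baseline"). This recovery has to come within 12 weeks, and the participant has to be clinically stable. The hepatitis C row then states: "otherwise, the participant should have a permanent full discontinuation of study interventions". The hepatitis B row says the same in almost identical words.
- **Same table, Other Causes row.** Restart is allowed "only if laboratory values have returned to Grade 1 or baseline (if normal or Grade 1 at start"), or on return to baseline grade, within 3 weeks.
- **Same table, immune-related hepatitis row.** Values must resolve to Grade 1 or lower, "or baseline (if abnormal at baseline").
- **Section 6.5.2, Cycle delay.** The general rule is that "such participants may be considered for treatment resumption once the toxicity resolves or improves to Grade 1 or baseline".
- **Section 8.3.8.** The ALT limits that define a Hepatic Event are split by baseline level ("Among subjects with Baseline ALT" below 2 × ULN, and at or above it), so raised baseline ALT is foreseen in this cohort.

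**The concern.** A rule of the form 'only if A or B, otherwise stop' sends every unnamed case to the stop. The two viral rows name a normal baseline and a Grade 2 baseline. Grade 1 lies between them and is in neither branch.

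The resulting order makes no clinical sense. A participant who moves from a normal baseline to Grade 1, which is worse than baseline, may restart. One who returns to a Grade 2 baseline may restart. One who returns fully to a Grade 1 baseline should lose both study drugs permanently. The protocol gives no reason for this.

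The case is foreseeable. Section 6.5.4.7 recognises that participants with chronic HBV or HCV can have virologic flares, and Table 9 itself contemplates a Grade 2 baseline. A site that follows the row literally would stop treatment in a recovered participant. A site that infers the intent would restart, so identical cases could be handled differently across sites.

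**Working it through.** No sample size, power or error rate is involved. The check is a truth table of baseline ALT grade against recovered ALT grade, assuming recovery within 12 weeks and clinical stability.

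**Inputs.** The restart sentence and its default come from the two viral rows of Table 9. Grades are normal (N), 1 and 2, taken on one scale at both times. Six outcomes end at or better than baseline: N→N, 1→N, 1→1, 2→N, 2→1 and 2→2.

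**Possible readings.** Two phrases are ambiguous.

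- The parenthesis about a normal baseline may qualify both 'normal' and 'Grade 1' (reading a), or only 'Grade 1' (reading b).
- Return to baseline grade may mean exactly that grade (reading x), or that grade or better (reading y).

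| Baseline → recovered | a+x | b+x | a+y | b+y | Proposed wording |
|---|---|---|---|---|---|
| N→N | restart | restart | restart | restart | restart |
| 1→N | stop | restart | stop | restart | restart |
| **1→1** | **stop** | **stop** | **stop** | **stop** | **restart** |
| 2→N | stop | restart | restart | restart | restart |
| 2→1 | stop | stop | restart | restart | restart |
| 2→2 | restart | restart | restart | restart | restart |
| Restart allowed | 2 of 6 | 4 of 6 | 4 of 6 | 5 of 6 | 6 of 6 |

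Only 1→1 is refused under all four readings, so the defect does not depend on how the sentence is parsed. N→1, which ends worse than baseline, is allowed under all four. With the same end grade, N→1 restarts and 1→1 stops.

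**Comparison with neighbouring rules for 1→1.**

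| Rule | Grade 1 baseline covered? | Result for 1→1 |
|---|---|---|
| Table 9, hepatitis B and C rows | No | Permanent discontinuation |
| Table 9, Other Causes row | Yes, named | Restart allowed |
| Table 9, immune-related row | Yes, any abnormal baseline | ALT condition met |
| Section 6.5.2 general rule | Yes | Resumption may be considered |

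Only the two viral rows leave the case out, which points to an omission and not to a deliberate choice.

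**A further consequence.** In the table as it reads, the management text for hepatitis C also serves the diagnosis of HCV relapse or new infection, which is triggered by HCV RNA and not by ALT. A participant whose ALT never left a Grade 1 baseline would then also fail the literal restart condition.

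**The case against.** The omission itself is hard to dispute. The case on the other side is about its weight.

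- **Discretion elsewhere in the protocol.** Section 6.5.4.7 presents the hepatic rules as guidance and uses 'should'. Section 6.5.3 says "The final decision on dose modification and/or corrective therapy will be based on the" investigator's judgment, and Section 6.5.1 says "Dose modifications different from those stated in the protocol should only be made in consultation with the Sponsor" (immediate safety aside). This does soften the effect. It does not supply a criterion for a Grade 1 baseline, and a general discretion clause sits awkwardly against a specific 'only if' instruction.
- **The general criterion as a fallback.** Sections 6.5.2 and 6.5.3 both accept recovery to Grade 1 or baseline, and the carve-out in 6.5.3 lists Tables 3-8, not Table 9. But ALT elevation and hepatitis are listed in Table 6, so they fall inside that carve-out. The general rule in 6.5.2 is less specific than the viral rows. The clause in 6.5.1 favouring the most conservative recommendation settles nothing either way, because it concerns several toxicities at once.
- **The grading scale.** The Table 6 footnotes grade ALT against baseline when baseline is abnormal, and Table 9 does not say which scale applies at recovery. The counts above therefore rest on a single scale. However, a Grade 2 baseline only makes sense when graded against ULN, and the branches are keyed to the baseline category. A different scale at recovery does not create the missing branch.
- **Implausible readings.** The low count of 2 of 6 requires a site to stop a participant whose Grade 2 baseline has improved, which few would do. That is fair, and the finding rests on the single outcome refused under every reading.
- **Few participants, and an error on the cautious side.** This stands in part. The cohort is about 40, and the case needs a viral hepatic event, a Grade 1 baseline and recovery to Grade 1 but not to normal. The literal rule adds no hepatic risk. Its cost is permanent loss of both drugs.

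**Conclusion.** The concern holds. As written, both viral rows send a participant who has recovered fully to a Grade 1 baseline ALT to permanent full discontinuation, under every reading of the sentence, while allowing restart at a worse Grade 2 baseline.

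The defect is one outcome out of six at or better than baseline. Up to three others (1→N, 2→N and 2→1) depend on the reading chosen. The number of participants affected cannot be derived: the protocol does not give the share with HBV or HCV and a Grade 1 baseline, and the master protocol's liver eligibility limits are not shown. That Grade 1 baselines are admitted is inferred from the explicit Grade 2 branch. No sample size, interval or stopping rule changes. This is a correction that should be made, and it does not threaten the trial's conclusions.

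**What to change.** Make two edits in both the hepatitis B and hepatitis C rows of Table 9, and leave the rest of each row unchanged:

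1. Extend the first parenthesis so that it covers a baseline that is normal **or Grade 1**, as the Other Causes row already does.
2. After the return to baseline grade for Grade 2 baselines, add **or better**. This is a separate clarification. It removes the reading under which a Grade 2 baseline that improves would be stopped.

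With these edits all six outcomes allow restart however the first parenthesis is attached, and N→1 stays allowed as now. The cost is a wording change to two sentences. No tests or visits are added, because ALT is already measured weekly under these rows.
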